6.2.3 Clinical Experience

The Step 1 (dose escalation in solid tumors) of the MEN1309-01 study, aiming to determine the MTD of MEN1309 in patients with CD205-positive advanced solid tumors is currently ongoing. The first patient has been treated on Oct 03rd, 2017. At the time Protocol Version 3.0 is issued, the dose cohort of 1.60 mg/kg has been successfully completed in Step 1, according to an ATD. As per protocol, the study design changed to an ascending dose cohort of 3+3 upon the occurrence of a DLT of febrile neutropenia which was observed in the first patients treated at 1.60 mg/kg. Consequently, this cohort has been expanded to six patients that have been treated and completed the DLT assessment period. Neutropenia grade 3/4 lasting \leq 7 days (and therefore not qualifying as DLT) was observed in all patient treated at 1.60 mg/kg as the only safety signal of clinical relevance; therefore the next cohort at 2.40 mg/kg dose level (i.e. with 50% higher ascending dose as per CRC decision) is open.

Considering that the dose cohort of 1.60 mg/kg has been successfully completed in Step 1, the first cohort of patients in Step 2 (dose escalation in NHL) is proposed to be open at 0.80 mg/kg (to be confirmed by the CRC).

6.2.4 Translational model-based strategy to support the choice of clinical doses for the first in human study

A translational model-based analysis has also been carried out to support the dosing regimen for the FIH clinical study. Allometric approaches were applied to (i) the monkey PK data to predict the human PK profile; (ii) a population PK/PD model, developed to scale the time-course of MEN 1309-induced neutropenia from monkey to patients; (iii) tumor growth inhibition data in mice, to identify the potential clinical effective dosing regimens. The risk-benefit profile of the proposed dosing schedule was evaluated based on predicted neutropenia and expected antitumor activity in patients.

This translational analysis supports the selected dosing regimen for the FIH study, namely the anticipated therapeutic dose range (ATDR) with 100% dose escalations from 0.05 to 6.4 mg/kg.

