8.2.1 Inclusion criteria

Patients meeting all the following criteria will be eligible for entry into the study:

1. Male or female patients aged ≥ 18 years.
2. For Step 1 of the study, patients with confirmed diagnosis of a solid tumor will be included based on the following characteristics:
 - Histological confirmed locally advanced or metastatic solid tumor, progressive after last treatment received and for which no standard curative therapy is available or the patient refuses standard therapy. For the purpose of this study, progressive disease is defined by RECIST v1.1.
 - Measurable or evaluable disease by Response Evaluation Criteria in Solid Tumors guideline (RECIST v1.1).
 - Availability of archived tumor material, either as a block or slides, which are locally assessed during the Pre-screening Period through immunohistochemistry (IHC) and show positivity ($\geq 1+$ IHC staining) for CD205. A new biopsy will be performed whenever possible upon patient's consent, during the screening period, if the archived tumor material is older than 3 months.
3. For Step 2 of the study, patients with NHL will be included based on the following characteristics:
 - Histological confirmed diagnosis of multiple relapsed or refractory NHL. Patient requires treatment because of NHL relapse following response to standard chemotherapy or high-dose chemotherapy + stem cell transplantation (SCT), or NHL is refractory [i.e., failure to achieve at least complete response (CR), partial response (PR) or stable disease (SD)] to its more

recent chemotherapy. Patient refuses standard therapy and is not eligible for autologous SCT (ASCT).

- Measurable or evaluable disease by Cheson Criteria (The Lugano Classification, 2014).
- CD205 positive NHL, locally assessed through IHC testing on the most recent archived tumor sample ($\geq 1+$ IHC staining) during the Pre-screening Period. A new biopsy will be performed whenever possible upon patient's consent, during the screening period, if the archived tumor material is older than 3 months.

4. Patients must be willing to receive transfusions of blood products.

5. Eastern Cooperative Oncology Group (ECOG) performance status (PS) of 0 to 2.

6. Neutrophil count within normal value; platelets $\geq 100,000/\mu\text{L}$; haemoglobin $\geq 9\text{ g/dL}$.

7. Adequate renal and hepatic laboratory assessments:

- creatinine $\leq 1.5\text{ mg/dL}$ or creatinine clearance $> 60\text{ mL/min}$
- bilirubin $\leq 1.5\text{ mg/dL}$

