8.5.4.5 Clinical Laboratory Evaluation

Safety laboratory assessments will be performed as reported in the sec. 2.2 and 2.3. β -HCG Pregnancy test will be performed, if applicable, during the Screening Period and will be repeated at each cycle before study drug administration, per local guidelines, and at the End of Study Visit. Urinalysis will be assessed at Screening, at each day of Visit 1, at Visit 2, at Visit 3 and at the End of Study Visit. The assessment of Anti-HIV Antibodies, Anti-HBcAg antibodies, Anti-HBsAg antibodies, HBV-DNA, HCV-RNA will be performed ONLY during Screening Period. Safety tests will be performed by the local laboratory of participating sites in order to ensure prompt patient management. For the same reason, tests for Anti-HIV Antibodies, Anti-HBcAg antibodies, Anti-HBsAg antibodies, HBV-DNA, HCV-RNA will be performed by local laboratory of participating sites according to local standard procedures. Results of laboratory tests for Anti-HIV Antibodies, Anti-HBcAg antibodies, Anti-HBsAg antibodies, HBV-DNA, HCV-RNA which have been performed within 3 months prior to Screening Period in the context of the standard patient's management (either in the local lab or in a different lab, provided that they comply with local standard procedures) can be reported in the electronic-Case Report Form (eCRF) under Screening Period procedures and in the patient file as a source document. In such a case, there is no need to repeat the above mentioned tests.

Laboratory values have to be transcribed into the eCRF, except for Urinalysis for which only the judgment has to be reported in the eCRF; the Sponsor will be provided with the currently valid version of the respective normal ranges by the site laboratories (any update of reference ranges needs to be notified on an ongoing basis).

The lab print-outs should be identified with the patient number. All print-outs should be dated and signed by the Investigator and stored in the patient's record. Any out of range value shall be clinically assessed by the Investigator.

The volume of blood to be drawn for each set of safety lab tests will amount to a maximum of 15 mL. The following tests will be performed:

Table 4: Blood and urine sample analyte listing

| BIOCHEMISTRY | SERUM VIROLOGY | HAEMATOLOGY | COAGULATION | URINALYSIS |
|--|---|---|--|---|

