9.3.4 Safety analysis

Safety analysis will be performed on the safety population through descriptive statistics during each study phase. Summary statistics will report the incidence of the AEs by CTC toxicity grade, dose level, relationship to study drug and overall. Counts and percentages will be reported for the results

of ECG, laboratory values, vital signs, physical examination, all classified as Normal/Abnormal Not Clinically Significant (NCS)/Abnormal CS by dose level and visit.

Descriptive statistics will also be produced for the extent of exposure, overall drug administration, drug administration by dose level and dose delay by dose level.

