A Treatment-Emergent SAE is defined as a TESS event classified as serious.

An AE will be classified as related to study drug if causality was recorded as “certainly related”, “probably related”, “possibly related”, “unassessable/unclassifiable”. Missing causality will be considered as related.

An overview of TESS will be provided with the number and percentage of patients reporting an event by cohort and overall for each period. The summaries will be presented for the following categories:

- Any TESS

- Any TESS by grade (<2, >=2)
- Any Serious TESS
- Any mild/moderate/severe TESS
- Any TESS leading to study drug discontinuation
- Any TESS leading to temporary study drug administration interruption
- Any related TESS (by categories)

If a patient has more than one occurrence of a TESS, the patient will be counted only once within that preferred term. The same applies to serious TESSs and drug-related TESSs.

Additionally, the following summaries of TESSs expressed as number and percentage of patients with TESSs will be presented by SOC and PT by cohort and overall, for each period:

- TESS
- Serious TESS
- Serious TESS resulting in death
- TESS of Grade >=2
- TESS of Grade <2
- TESS by intensity (by categories)
- TESS leading to study drug discontinuation
- Serious TESS leading to study drug discontinuation

Drug-related TESSs will be summarized in the same way that TESS as it is described above.

Moreover, the following summary will be presented for drug-related TESS:

- Number of events, number of patients and percentage of patients with DLT by SOC and PT

In the final TFL a summary of TESSs by period and Grade will be reported.

All adverse events (including non-TESS or AEs happening after End of Study Visit of the patient) recorded on the eCRF will be listed. A separate list of serious adverse events will be provided. TESS will be flagged in the listings.

Laboratory data

All laboratory data will be listed.

Clinical chemistry, haematology and urinalysis parameters will be summarized by parameter, visit and cohort using descriptive statistics. The change from baseline will be summarized for each post baseline visit with descriptive statistics by cohort and visit.

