Summary statistics will also include the number and percentage of patients with Normal, Abnormal NCS (Non Clinically Significant) or Abnormal CS (Clinically significant), by parameter and visit. Shift tables will be presented with the counts of individual shifts from each of the reference range categories from baseline to post-dose by laboratory parameter, cohort and visit.

All laboratory data will also be reported in listings.

Previous/ Concomitant medication

All medication taken within 30 days before enrolment and taken during the study will be listed. Medication will be coded using the WHO drug dictionary (version C_DD_Jun2012-WithPrefTerm) and summarised by PT and by anatomical therapeutic chemical (ATC) category level X.

Previous medications are those which start within 30 days prior to enrolment and stopped prior to first dose of study drug. Concomitant medications are those which are started on or after date of first induction, or started prior to induction and stopped after or are ongoing.

The number and percentage of patients of previous and concomitant medication will be tabulated and summarized for concomitant medications.

Any previous and concomitant medication record will also be presented in a listing.

Electrocardiogram (ECG) Evaluations

ECG judgment collected on the eCRF will be summarised descriptively by cohort and visit. Similarly, changes from baseline for each post baseline visit will be summarised.

Vital Signs Evaluations, weight

Vital signs (systolic and diastolic BP (Blood Pressure - mmHg), weight reported in kilograms (kg), heart rate), will be summarised descriptively by cohort and visit. Similarly, changes from baseline will be summarised for all scheduled post baseline visits.

All vital signs parameters will be listed.

Physical Examinations

Physical examination findings (Normal, Abnormal NCS or Abnormal CS) will be summarised using descriptive statistics by Body System, cohort and visit.

Abnormal NCS or Abnormal CS findings on physical examination will be presented in a listing.

Efficacy Analyses

During CRC meeting no efficacy data can be analyzed since efficacy assessment (MRI TC PET scan) will be repeated every 2 cycle.

The efficacy will be evaluated at the end of the study.

Pharmacokinetics Analysis

Pharmacokinetics section will be present upon availability of laboratory data.

Plasma concentrations will be reported for each time point.

PK parameters will be reported with:

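### The SAP plans no CTCAE-graded laboratory table, so no planned table clearly counts patients with grade 3 or grade 4 neutropenia, or its duration, by dose level

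*SAP*

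**What the plan says.** SAP 6.1.1.2 (Laboratory data) plans four outputs:

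- Numeric summaries and change from baseline: "Clinical chemistry, haematology and urinalysis parameters will be summarized by parameter, visit and cohort using descriptive statistics". The standard statistics in the same section include the median, minimum and maximum.
- Counts of judgements: "number and percentage of patients with Normal, Abnormal NCS (Non Clinically Significant) or Abnormal CS (Clinically significant), by parameter and visit". Protocol 9.3.4 has the same scale, with results "all classified as Normal/Abnormal Not Clinically Significant (NCS)/Abnormal CS by dose level and visit".
- Shifts: "Shift tables will be presented with the counts of individual shifts from each of the reference range categories from baseline to post-dose".
- Listings of all laboratory data.

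Adverse events are graded. The overview has two groups, "Any TESS by grade (<2, >=2", and the same split is repeated by SOC and preferred term (PT), by cohort and period, and again for drug-related events. Intensity (mild, moderate, severe) is also tabulated by SOC and PT, as are DLTs. One further summary by period and grade is promised for the final output, with no mention of PT. Protocol 9.3.4 plans AE incidence by CTC grade and dose level.

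Protocol 6.2.3 reports that grade 3/4 neutropenia of 7 days or less "was observed in all patient treated at 1.60 mg/kg as the only safety signal of clinical relevance". Inclusion criterion 6 (Protocol 8.2.1) requires "Neutrophil count within normal value".

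**The concern.** The laboratory DLT criteria (SAP 5.1.1.1, Protocol 8.5.5.1) use grades or ULN multiples: grade 3 or higher for troponin, bilirubin, transaminases and ALP (at least 10 × ULN for transaminases or ALP that were grade 2 at baseline), grade 4 for platelets and haemoglobin, and grade 4 neutropenia of more than 7 days (more than 5 with mandatory growth factor). The laboratory tables sort the same values on two other scales, one coarser and one subjective.

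The toxicity profile is a secondary objective, and Protocol 6.3 names neutropenia as the most frequent adverse reaction. A reader of the study report will want to know, at each dose, how many patients reached grade 3, how many reached grade 4, and for how long. No planned table is clearly committed to answering that from the measured values.

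**Working it through.** No formula or stated figure is involved. The check compares each planned output with what the DLT criteria need.

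| Planned output (SAP 6.1.1.2) | Scale | Counts grade 3 and grade 4 separately by dose? |
|---|---|---|
| Laboratory shift table | Reference range | No |
| Laboratory judgement counts | Normal / NCS / CS | No |
| Laboratory numeric summary | Mean, median, minimum, maximum | No; shows typical and extreme values |
| Laboratory listing | Individual values | Not tabulated; derivable by hand |
| AE by SOC and PT | Grade <2 / ≥2 | No; grades 2, 3 and 4 together |
| AE by SOC and PT | Mild / moderate / severe | No; different scale |
| AE by period and grade | Grade | Not stated to be by PT |
| DLT by SOC and PT | DLT yes/no | Only events already declared |

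**Neutrophils.** Criterion 6 makes the baseline normal, and eligibility is re-checked on Day 1. A post-dose count below range is therefore always normal-to-low. With six patients at 1.60 mg/kg, all grade 3/4, the table shows 6/6 normal-to-low at any visit where all six are low. Six grade 1 falls would give the same 6/6.

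**Liver enzymes.** Criterion 7 admits transaminases up to 5 × ULN when hepatic metastases are present. A patient who enters at 5 × ULN and reaches 10 × ULN, the level named in the DLT definition for patients with grade 2 values at baseline, has doubled (10/5 = 2) but is counted as high-to-high. In a patient who enters in range, values of 1.1 × ULN and 9 × ULN fall in the same cell.

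**Units.** Safety tests are run locally at approximately 8 sites, and Protocol Table 4 lists troponin I or T. Raw summaries can therefore combine different assays and different ULNs. Protocol 8.5.4.5 has numeric values entered in the eCRF and normal ranges sent to the sponsor, so rescaling to the local ULN is possible.

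**The AE route.** Under Protocol 8.6.4 a laboratory abnormality is to be reported as an AE when the investigator considers it of clinical relevance. AE tables are therefore not an independent count of graded values.

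**Duration.** No planned table gives the duration of grade 4 neutropenia. In Cycle 1 the scheduled haematology days after Day 4 are 8, 11, 15 and 18. If grade 4 is seen on Days 11 and 15 but not on Days 8 or 18, it lasted at least 15 − 11 = 4 days and less than 18 − 8 = 10 days. That range spans both the 5-day and the 7-day thresholds, so the derivation needs a written rule.

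**The case against.** The strongest reply is that the plan already carries much of this information. It does, and several stronger readings fail as a result.

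- A reader might infer that no SAP table can tell grade 1 from grade 4 neutropenia. That is true only of the laboratory categorical and shift tables. Reported as AEs, the two grades fall on opposite sides of the grade 2 split by SOC and PT.
- A reader might infer that depth by dose cannot be seen at all. The median and lowest neutrophil count by visit and cohort are planned. They do not say how many patients reached each grade.
- A reader might infer that DLT-grade values go unchecked. The investigator assesses each out-of-range value, the sponsor reviews laboratory abnormalities bi-monthly, source data verification is 100%, and the Cohort Review Committee sees all available safety data before escalation. Protocol 6.3 shows that neutropenia at 1.60 mg/kg was captured and graded. What is missing is a planned output that reconciles values with declared DLTs.
- A reader might infer that days within a visit are pooled, for example Days 8 and 11. The SAP does not say so: it refers to the time points of the schedule, and Protocol 9.3.1 to each time point. Days 8 and 15 belong to different visits.
- A reader might infer that the urinalysis table is impossible, since values are recorded "except for Urinalysis for which only the judgment has to be reported in the eCRF". Descriptive statistics in the SAP also cover categorical variables, so they can apply to the judgement.
- Neutropenia is one of eight DLT criteria and not the whole definition, although the one DLT reported up to 1.60 mg/kg was febrile neutropenia.

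**Conclusion.** The concern holds in limited form. No laboratory output applies a CTCAE grade, the AE tables by PT stop at a split at grade 2, and no planned table clearly counts patients with grade 3 or grade 4 neutropenia, or the duration of grade 4, by dose level. The same gap applies to the other graded laboratory DLT analytes. The practical size is the 1.60 mg/kg example: six of six patients with grade 3/4 neutropenia could look the same in the shift table as six with grade 1.

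This is a worthwhile and cheap improvement to descriptive reporting in a phase I trial. It does not show that any DLT was missed or that the MTD rule is unsound. One limit: in the text available, SAP 8.1.1.3 (list of tables and figures) is a heading without content, so a graded table in the shells cannot be ruled out.

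**What to change.** In SAP 6.1.1.2, for analytes that have a CTCAE v4.03 grade:

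- Derive the grade from each numeric value and the local reference range.
- Tabulate worst grade and the shift from baseline to worst grade by dose level, for Cycle 1 and for all cycles, in addition to the reference-range shift or in its place.
- Report neutrophil nadir, day of nadir and duration of grade 4 neutropenia, with a rule for the gaps between samples (for example, shortest and longest duration consistent with the data).
- Express bilirubin, ALT, AST, ALP and troponin as multiples of the local ULN, with troponin I and T shown separately.
- State that laboratory summaries are by scheduled day, and that urinalysis summaries use the recorded judgement.
- List every value that meets a laboratory DLT threshold beside the declared DLTs.
- State that the AE summary by period and grade is by PT and dose level, in line with Protocol 9.3.4.

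The cost is SAP text and some extra programming; no new data are needed. It is best settled before database lock, because Protocol 9.5 treats analyses that were not pre-specified and are run after lock as additional or exploratory.

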6.1.1.3. ANALYSIS POPULATIONS

The following analysis population will be considered:

DLT population

All patients receiving at least 75% of the first scheduled study drug administration and with a safety follow-up of 21 days after the administration. Patients enrolled in the dose escalation phase who are not DLT evaluable will be replaced.

Safety population

All patients receiving at least 1 dose of study drug.

Efficacy population

All eligible patients who receive at least 2 complete treatment cycles and have at least 1 disease assessment are to be considered evaluable for efficacy.

Per Protocol population

All patients of the efficacy population excluding patients who experience major protocol violation(s) that may affect the efficacy analyses.

PK population

All patients receiving study drug and with reliable drug assay data relevant for the PK parameter of interest.

6.1.1.4. DETERMINATION OF SAMPLE SIZE

As first estimation, approximately 122 evaluable patients are expected to be enrolled in the clinical research study: 100 in Step 1 (including 25 patients to be receive MEN1309 in the Expansion Cohort) and 22 in Step 2; however, the total number of evaluable patients depends upon the number of doses and patients by dose cohorts to establish the MTD in Step 1 and Step 2.

It is anticipated that approximately 20% of patients will not pass successfully the Screening Visit. Patients who drop out prior to be evaluable for DLT during the dose escalation will be replaced.

7. GENERAL DEFINITIONS

7.1.1.1. DATA VALIDATION

Medidata Classic Rave 2019.1.0 will be used, as Electronic Data Capture system for data entry, by site personnel and for data cleaning and data locking by the Menarini Data Management team.

7.1.1.2. COMPUTER SYSTEMS AND SOFTWARE TO BE USED IN THE ANALYSIS

SAS v.9.3 (or upper) by SAS Institute Inc., Cary, NC, USA.

Database and SDTM and ADAM datasets will be created by using SAS Clinical Data Integration Studio version 4.9.

All tables and listings will be produced using PROC REPORT or procedure specific output displays using output delivery system (ODS) within SAS version 9.3 (or upper) and using SAS Office analytics.

7.1.1.3. CODING SYSTEMS USED

Clinical Terms

Concomitant diseases, medical procedures, and AEs will be coded with MedDRA 22.0

Drugs

Drugs will be coded with WHODrugGlobalB3 201903

8. TABLES FIGURES AND LISTINGS

8.1.1.1. STATISTICAL ANALYSIS REPORT (TFL)

The TFL (Tables, Listings and Figures) will follow the list of tables, plots, and listings of section 6.3 and 6.4, which are intended to provide the overall idea of the general output and ordering of the TFL and will not necessarily be reproduced in the final TFL document.

8.1.1.2. TABLES, HEADINGS, AND FOOTNOTES

All tables stratified by treatment and gender will also contain the treatment overall column. The tables repeated for analysis population will be produced only once if the analysis populations are identical. All tables are provided for ITT population unless specified otherwise.

Line 1: Study code: DELA-01

Line 3: *Table/Listing/Figure n: Table name (Study population)*

Line 4: *Table/Listing/Figure n.n: Table name*

Line 5: *Table/Listing/Figure n.n.n: Table name [if applicable]*

Line 6: *Table/Listing/Figure n.n.n.n: Table name [if applicable]*

Line 7: *Table/Listing/Figure n.n.n.n.n: Table name [if applicable]*

Footnote: *Relevant notes (if any)*

